FTE	Full Time Equivalent
FTP	Secure File Transfer Protocol
HCSRN	Health Care Systems Research Network
HIPAA	Health Information Portability and Accountability Act
IRB	Institutional Review Board
KP	Kaiser Permanente
KPWA	KP Washington
KPWHRI	KP Washington Health Research Institute
MHRN	Mental Health Research Network, HCSRN
NIMH	National Institute of Mental Health, NIH
ODD	Oppositional Defiant Disorder
OHRP	Office of Human Research Protections
PAL	Partnership Access Line
QMP	Quality Management Plan
SAE	Serious Adverse Event/Serious Adverse Experience
SUAY	Safer Use of Antipsychotics in Youth
TMH	Telemental Health

PROTOCOL SUMMARY – SUAY PRAGMATIC EFFECTIVENESS TRIAL

Title:	A Pragmatic Effectiveness Trial: Safer Use of Antipsychotics in Youth (SUAY)
Précis:	
A pragmatic encouragement trial will test the effectiveness of an intervention aiming to improve the targeted and safer use of antipsychotic medications by guiding clinician-prescribing behavior of antipsychotics for children aged ≥ 3 and < 18 years and encouraging psychosocial therapy for eligible youth. The intervention includes a medication best practice alert in Epic, consultation with a child and adolescent psychiatrist, and extra support for patients and families to improve behavioral health service access. The trial will be conducted in multiple health systems. Each health system will randomize prescribers to one of two study arms, intervention and control. During patient encounters, entering an antipsychotic for a potentially eligible patient will cause either the control or intervention medication alert to fire in the electronic medical record. The control arm medication alert will point prescribing clinicians to relevant Choosing Wisely[®] recommendations. The intervention arm medication alert will inform prescribers that:
 
 1. Antipsychotics are not recommended 1st line treatment for non-psychotic disorders; 2. A child and adolescent psychiatrist (CAP) will review antipsychotic usage by youth; 3. Expedited access to bridging therapy, behavior health navigation, and/or a proactive consultation with a CAP may be ordered. 
The intervention medication alert will point prescribing clinicians to both Choosing Wisely[®] recommendations and clinical guidelines for SUAY. Analytic data will be collected from automated data sources at the health systems. The primary outcomes are percent of children taking an antipsychotic medication at 6 months of follow up, and total person-months of antipsychotic use among participants during the study period – based on medication order data.

Objectives:	Test the effectiveness of the intervention treatment algorithm vs. usual care control in a practical clinical trial involving several hundred subjects in multiple health systems.
Populations:	
Providers authorized to order prescription medications in the health system’s electronic medical record.
 
Patients aged ≥ 3 and < 18 years without diagnosed psychosis, mania, autism spectrum disorder, or intellectual disability.

Number of Sites:	
 1. Kaiser Permanente Washington 2. Kaiser Permanente Colorado 3. Nationwide Children’s Hospital 4. Kaiser Permanente Northwest

Description of Intervention:	
The intervention arm medication alert prompts the prescriber to (a) keep/remove the antipsychotic order, and/or (b) order behavioral health (BH) navigation, and/or (c) order expedited access to psychotherapy (e.g., telemental health bridging) for the patient/family, and/or (d) order a provider-to-provider virtual consult with a child and adolescent psychiatrist (CAP).
 
Case review by a child and adolescent psychiatrist will automatically occur for all eligible intervention arm patients. A provider-to-provider consult will be scheduled if either (a) the prescriber ordered the consult or (b) the CAP needs to discuss the case with the prescriber to complete his/her review.
 
Following review by the CAP, a BH navigator messages the prescriber and reaches out to the eligible intervention arm patient/family to offer extra support (unless actively declined by the prescriber or CAP). The navigator's role is to (a) provide extra support to facilitate access and engagement in appropriate psychosocial therapies; (b) coordinate short-duration bridging therapy sessions for teens/families not engaged in psychotherapy, when appropriate; and (c) keep the prescriber informed of any clinically relevant updates.

Trial Duration:	30 months
Subject Participation Duration:	Up to 30 months for clinicians 6 months for patients
Estimated Time to Complete Enrollment:	24 months

Schematic of Study Design:

2 INTRODUCTION: BACKGROUND INFORMATION AND SCIENTIFIC RATIONALE

2.1 Background Information

Beginning in the mid 1990's, rates of prescribing antipsychotic medications to children and adolescents grew tremendously (1-6) and remain high in both Medicaid and commercially insured populations (6-9). Most antipsychotic medications prescribed to children are "second generation" or "atypical" antipsychotic medications. We will refer to these simply as antipsychotics. These medications are argued to have milder side effect profiles (e.g., reduced extrapyramidal symptoms) than older "first generation" or "typical" antipsychotic medications. However, the side effects of newer APs can still be severe (10, 11). The side effect profiles of individual medications in the same class differ significantly and their impact on the individual patients who take them are also known to differ (12-14).

The vast majority of antipsychotic use in youth aged 5-17 years is for non-psychotic disorders and is particularly prevalent in youth with a diagnosis of attention deficit hyperactivity disorder (ADHD) with comorbid conduct disorder (CD) or oppositional defiant disorder (ODD) and/or impulsive aggression (7, 15, 16). For example, we analyzed a sample of 562,423 youth prescribed psychotropic medications in our Mental Health Research Network (MHRN), a consortium of 13 health care delivery systems across the U.S., including 11,095 with at least one prescription for an antipsychotic medication, during the year 2011 alone. In this sample, 66% of boys aged 6-11 years that were prescribed an antipsychotic medication had a diagnosis of ADHD and CD or ODD and did not have a psychotic disorder or other FDA-approved indication. (See Penfold *et. al.*, 2013 for a detailed breakdown of antipsychotic medication use in MHRN.)

In its *Choosing Wisely*[®] recommendations, the American Psychiatric Association lists as its 5th recommendation: ***Don't routinely prescribe an antipsychotic medication to treat behavioral and emotional symptoms of childhood mental disorders in the absence of approved or evidence supported indications***(17). However, not all antipsychotic prescribing for emotional and behavioral disturbances is inappropriate. It may be reasonable for clinicians to prescribe antipsychotics when youth are a danger to themselves or others and/or not responding to primary treatments in the absence of a psychotic disorder. Nevertheless, a new and updated algorithm and workflow is needed to guide clinicians regarding when and how to prescribe antipsychotic medications to youth with non-psychotic disorders. Importantly, there are a number of reasonable algorithms for antipsychotic prescribing to youth(18-23); however, there are two fundamental gaps in our understanding of how to implement such guidelines: (a) how to support clinicians most effectively in following the algorithms and (b) how to increase access to psychosocial primary treatments that all of the existing guidelines recommend as part of first line treatment (in addition to non-antipsychotic medications). A new algorithm will be largely ignored unless we address the fundamental issues of implementation(24-31) and long known barriers to changing prescribing practices addressed in the academic detailing literature(32-39).

In phase 1 of SUAY, a sequenced treatment algorithm and clinical workflow were developed. The study is inspired by the highly successful Partnership Access Line (PAL) and Second Opinion program operated for the Washington State Medicaid program. Implementation of this program in Washington resulted in

a 50% reduction in antipsychotic medication use among Medicaid insured youth over its first four years. Second Opinion reviews have previously generated a 51% decrease in outlier ADHD stimulant medication prescribing, coupled with a 10:1 return on investment(40). Similar peer consult programs have been demonstrated effective in other settings.(41, 42) In its current form, this program requires an outpatient pharmacist to hold a prescription awaiting Medicaid authorization for an antipsychotic outside of an established state guideline until there is documentation of a consult between the prescribing provider and a child and adolescent psychiatrist (CAP) at Seattle Children’s Hospital. Providers can also electively reach out to the team’s consultants via the PAL service line to discuss best practice care in a state-wide rapid access program staffed by 1.5 FTE of CAP time.

Further success and spread into community settings will require understanding and supporting provider, patient and caregiver needs at the point of care when therapies are first being considered and discussed. The core elements of our proposed intervention are: (a) sequenced ‘treatment alternatives’ algorithm based on best evidence that accommodates diversity of practice; (b) effective clinical decision support (including human consultation) integrated into the flow of practice; (c) behavioral health navigation for psychosocial treatment alternatives that are effective and acceptable to families; and (d) expedited access to evidence-based psychosocial therapy.

2.2 Rationale and Objectives

Antipsychotics are prescribed to children for a number of behavioral health conditions despite lack of FDA approval or evidence of their effectiveness or safety. Such ‘off label’ use of antipsychotics exposes children to significant health risks. The SUAY trial aims to minimize use of antipsychotics to treat non-psychotic behavioral disturbances in children in four real-world health care systems.

The pragmatic encouragement trial will assess the effectiveness of an intervention aiming to improve patient safety by guiding clinician prescribing behavior of antipsychotics for children ≥ 3 and < 18 years old. The intervention includes a provider-facing medication alert in Epic and case review by a child and adolescent psychiatrist and extra patient-facing support to improve behavioral health service access (e.g., navigation, TMH).

3 OUTCOME MEASURES

Outcome measures will be collected regardless of the extent to which intervention arm clinicians, patients, or families accepted or utilized interventional components. That is, we will follow an intent-to-treat approach and encouragement trial methods.

3.1 Primary

The following primary quantitative outcome measures for the trial will be assessed for the contract deliverable:

- Percent of youth using antipsychotics at 6 months, measured by medication orders placed within the health system during the 180 day follow up period;
- Total person-months of antipsychotic use by youth, measured by medication orders placed within the health system during the 180 day follow up period.

3.2 Secondary

The following secondary quantitative outcome measures for the trial will be assessed:

- Percent of youth using antipsychotics at 6 months, measured by prescription fill data available for the 180 day follow up period;
- Total person-months of antipsychotic use by youth, per prescription fill data available for the 180 day follow up period.
- Emergency department/urgent care visit frequency, both for psychiatric crises and for other reasons;
- Percentage of baseline and follow-up safety assessments (i.e., BMI measurement and laboratory results);
- Percentage of clinicians that follow CAP advice according to algorithm;
- Modal stage at departure from algorithm (first line, second line, third line treatment prior to antipsychotic);
- Percentage of patients with change to psychotropic medication treatment plan following second opinion review;
- Percent of patients that agree to behavioral health (BH) navigation;
- Percentage of patients attending two or more system-provided therapy sessions;
- Percentage of patients attending two or more study-provided therapy sessions;
- Of patients in study therapy, percentage who subsequently attend two or more system-provided therapy sessions.

4 TRIAL DESIGN

We will conduct a two-group pragmatic encouragement clinical trial comparing the intervention and control at multiple sites. The follow up period for the trial will be 6 months.

5 STUDY ENROLLMENT AND WITHDRAWAL

5.1 Prescribing Clinicians: Inclusion and Exclusion Criteria for Provider Subjects

A site programmer will randomly assign providers to one of two study arms prior to fielding. Randomization determines which study medication alert the provider will receive. Intervention arm providers have the ability to order extra support from the study:

- A provider-to-provider consult with a child and adolescent psychiatrist (CAP), and/or;
- Behavioral health navigation for the patient/family , and/or;
- Expedited access to psychotherapy (e.g., telemental health) for the patient/family.

All randomized providers will receive advance notification of the study launch. Providers in the intervention arm will be told about the extra support that may be ordered and given a web-link to the expert clinical guidelines developed for SUAY. The control arm providers will be informed that a research study is being conducted to improve the quality of antipsychotic medication prescribing.

Inclusions:

- Clinician is credentialed to order prescription medications in the health system's electronic medical record (EMR).

Exclusions:

- Clinician practices outside of the delivery system (e.g., external or network provider).

5.2 Patients and Families: Inclusion and Exclusion Criteria for Patient Subjects

Potentially eligible patients are logged for study enrollment at the time the medication alert fires. Patients are assigned to the study arm of the randomized prescribing provider. Local study staff will blindly confirm eligibility via medical record review for all intervention and control arm patients logged for eligibility review and enrollment.

Inclusions:

- Patient is ≥ 3 and < 18 years of age at the time of the encounter at which the study alert fired;
- Study service (BH navigation, bridging therapy, CAP consult) ordered in Epic for the patient;
 - The BPA allows providers to remove the antipsychotic order and still order services.
- Patient is initiating a new episode of outpatient treatment with an antipsychotic medication.
 - New episodes are defined by no record of an antipsychotic medication being ordered within the health system as part of an outpatient care plan in the prior 180 days.

Exclusions:

- Patient has a diagnosed psychotic disorder, mania, autism spectrum disorder, or intellectual disability;

- Patient was enrolled in the SUAY pilot study;
- The antipsychotic entered is prochlorperazine (Comazol®) – which is used to treat nausea;
- An outpatient antipsychotic order is entered by a temporary provider in the health system. For example, a “doc of the day” signing an order initiated by a pharmacist transferring an existing prescription to the health system. This situation may also occur when a temporary provider signs a medication order for a prescription initiated in an inpatient setting as part of a discharge plan.
 - Note that orders placed by temporary providers do not count towards the 180 day medication free period for defining a new episode of care.
- The antipsychotic order was placed within an urgent care, emergency department, or inpatient setting (to avoid intervening during a crisis).
 - Note that orders placed in these settings do not count towards the 180 day medication free period for defining a new episode of care.
- Primary language is not English (e.g., patient requires a translator).

5.3 Provider Randomization Assignment Procedures

5.3.1 Randomization Procedures

Randomization will occur before the trial begins. All eligible providers will be block randomized to ensure comparable numbers of patients enrolled in each study arm. Providers will be categorized according to the expected number of patients for whom they will issue a qualifying prescription during the study period. The expected number of qualifying prescriptions will be determined given past prescribing behavior and department or specialty. Information on past prescribing behavior may vary across study sites based on available provider data but will generally include the absolute number of qualifying prescriptions as well as the rate of qualifying prescriptions (per number of visits billed or number of unique patients seen, as available). Providers in certain departments may also be more likely to write qualifying prescriptions. For example, providers who specialize in mental or behavioral health or providers in clinics focusing on higher risk adolescents. The particular departments associated with more qualifying prescriptions will be identified separately for each health system based on previous prescribing patterns and knowledge of that health system.

Providers in each health system will be divided into as few as two randomization blocks (likely and unlikely prescribers) and as many as four randomization blocks (unlikely, likely, high frequency, and very high frequency) based on the total number and distribution of expected number of qualifying prescriptions. For example, KP Washington providers wrote fewer than 100 qualifying prescriptions in the yearlong interval examined and the distribution of qualifying prescriptions per provider had a long right tail indicating that a small number of physicians wrote a large number of qualifying prescriptions. In this

context, we defined four groups for block randomization to protect against a large imbalance in the number of patients enrolled across study arms.

R, an open-source statistical computing software, will be used to generate an even number of control and intervention assignments within each provider block.

Providers hired after initial randomization will be assigned to the unlikely or likely prescribing randomization blocks based on hiring department. Randomization schedules will be generated for unlikely and likely prescribing blocks, and randomization arms will be assigned sequentially as new providers are hired. Providers previously randomized for the phase 2 pilot will remain in the arm assigned for the pilot.

5.3.2 Blinding

Study staff will be blinded to study arm when verifying subject eligibility.

The details of the study design will not be known by clinicians delivering treatment or writing prescriptions or orders (i.e., outcome assessments will be blinded).

Study child and adolescent psychiatrists, behavioral health navigators, and therapists only interact with intervention arm subjects. Group assignment is therefore known to these study staff.

The PI and Site Clinical Investigators will remain blinded to arm assignment until follow-up is complete. Only data coordinating center staff will be un-blinded to arm when preparing harm reports for the DSMB). Investigators will be un-blinded for reporting any intervention arm incidental deaths to the NIMH DSMB, should such events occur during the course of the trial.

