5.5 Opting Out of Study Components

Medication alert: Providers may cancel the medication alert by both de-selecting the antipsychotic in Epic and not ordering any extra support (i.e., CAP consultation, BH navigation, expedited psychotherapy access).

CAP review: Intervention arm prescribers may not opt out of passive CAP reviews. Control arm prescribers are not included in CAP review.

- The CAP is automatically informed of the need for a passive review (i.e., provider did not order a consult) after eligibility is confirmed.
- The CAP is automatically informed of the need for an active review (i.e., provider ordered a consult), prior to eligibility confirmation to avoid any delay.
 - If the patient is deemed ineligible upon review, other study services will not be offered to the patient/family.
- Passive CAP review will still occur if the clinician clicked an exclusion in the BPA (e.g., autism) and the patient is subsequently verified to be eligible. That is, study staff (not the prescriber) determines study eligibility. The prescriber maintains his/her clinical autonomy and may opt not to follow the CAP's treatment recommendations. No treatments or medications are withheld at any time.

CAP consultation: The study CAP may still reach out to an intervention arm prescriber to discuss a case when a CAP consult was not ordered. The prescriber may decide not to respond to or schedule with the CAP. The prescriber maintains his/her clinical autonomy and may opt not to follow the CAP's treatment recommendations. No treatments or medications are withheld at any time. Secondary outcomes include: the percentage of clinicians that follow CAP advice; the percentage of patients with a change to psychotropic medication treatment plan following CAP review; and model stage of departure from the algorithm (first line, second line, third line treatments prior to antipsychotic).

Behavioral health navigation: Intervention arm providers may decline behavioral health navigation for their patient by responding to a staff message from the navigator. Families/teens contacted by the navigator may decline behavioral health navigation at any time. Secondary outcomes include the percentage of patients that agree to behavioral health navigation, and the percent of patient that attend 2 or more face-to-face therapy sessions.

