7 INTERVENTION ARM

7.1 Intervention Arm Medication Alert Intervention Description

Randomized providers at each site will be informed in advance of the quality improvement study being conducted. The communication will inform intervention arm providers of the nature of the interventional components (e.g., medication alert, case review by a child and adolescent psychiatrist, behavioral health navigation, bridging therapy).

The medication alert is triggered by entering an antipsychotic in Epic for a target patient. See Appendix B. The patient is added to a study enrollment log at the time of the encounter. The intervention arm medication alert links providers to a document containing *Choosing Wisely*[®] guidelines, the national expert consensus panel clinical guidelines developed for SUAY, and contextual study information.

Within the alert, the prescriber has the option to:

- keep/remove the medication entered (default = remove)
- keep/remove an order for a provider-to-provider consult with the CAP (default = keep)
- keep/remove an order for BH navigation for the patient (default = keep)
- keep/remove an order for expedited access to bridging therapy for the patient (default = keep)

The study CAP is automatically notified that a review is needed each time an intervention arm provider actively orders a CAP review in the alert and after a patient is verified eligible when a consult is not actively ordered.

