7.2 Eligibility Confirmation

Study staff (PI or delegate) blinded to arm assignment will conduct a focused medical record review within 3 business days of the case being logged to the study when the alert fired. The staff person will utilize a checklist of study inclusion and exclusion criteria for this review.

Patients found not to meet criteria will be flagged as ineligible and the reason(s) noted in the study log. Patients found to meet all study criteria will be flagged as eligible. Upon being thus flagged, eligible intervention subjects will be ‘released’ to the CAP and navigator.

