7.3 CAP Case Review and Consultation Intervention Description

Expert clinical guidance for safer prescribing of antipsychotics to youth was developed in Phase 1 of the contract. See Appendix C. This will guide the CAP as s/he reviews the clinical scenario around each antipsychotic order (e.g., treatment history, current treatments, diagnoses) to determine the next best step in the treatment plan. If information is missing or the prescription is not in line with expert clinical guidance, the CAP may attempt to contact the prescriber to discuss the appropriateness of proceeding to an antipsychotic for the case and possible revisions to the treatment plan. The CAP will provide the prescriber with a written recommendations summary for every review completed. A standardized template will be used. The CAP’s recommendations may be noted in the medical record.

The prescriber is free to accept or disregard the CAP's recommendations. There are no negative consequences to providers if CAP treatment recommendations are not implemented. That is, the prescriber's clinical autonomy is in no way constrained or diminished.

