Hypothesis-generating exploratory subgroup analysis will be the Heterogeneity of Treatment Effects (HTE), conducted using adjustment variables in the model. To perform HTE analyses, we will use the same analysis procedure for the primary outcome but now including adjustment variables indicated below separately, with an interaction term between the treatment and the covariate. HTE analyses are prespecified for: provider type (MH vs. non-MH), gender, age, race/ethnicity (composite variable), new health plan enrollee, insurance type (Medicaid vs. non-Medicaid) and whether participant had an exclusion diagnosis in year prior to baseline.

Variables	Definition	Present/Absent
taking_at_6mon	Using AP at 6 months (No (0)/Yes(1))	present
group	Randomization Group – use for restricted descriptive stats (Intervention/Control)	present
group_cat	Randomization Group	present

Analysis plan for Safety Use of Antipsychotics in Youth (SUAY)

	(Control (0)/Intervention (1))	
prior_hosp	Prior Hospitalization (No (0)/Yes(1))	present
provider_type	Provider type of the enrolling provider, based on specialty (Non-Mental Health (0)/Mental Health (1))	present
age_emanicip	Emancipated age according to state (No (0)/Yes(1))	Present
gendern	Gender (Male (1)/Female (2))	Present
race_white_NH	Race - White non-Hispanic (only) (No (0)/Yes(1))	present
insuranceType	Type of insurance Commercial/Medicaid/Other	present
exclusion	Exclusion diagnosis in year prior to baseline	Needs to be created using baseline dx variables
new_enrollee_1	new health enrollee (1 st definition) Yes/No	present
new_enrollee_2	new health enrollee (2 nd definition) Yes/No	present

Primary analysis II

Our primary analysis examines antipsychotic medication (AP) use, as measured by days' supply ordered, in the 6 months following patient enrollment.

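### As written, the eligibility review is not reliably blind to arm: the checklist and chart can show items that only intervention patients have, and the exclusions follow arm assignment

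*Protocol*

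**What the plan says.** Protocol 5.3.2 states: "Study staff will be blinded to study arm when verifying subject eligibility". Sections 5.2 and 6 repeat the claim. Section 5.3.2 also keeps the PI blinded until follow-up has ended. Section 7.2 gives the procedure: "Study staff (PI or delegate) blinded to arm assignment will conduct a focused medical record review within 3 business days" of logging, and "The staff person will utilize a checklist of study inclusion and exclusion criteria for this review".

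Other sections determine what the chart holds at that time:

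- Section 5.2 lists among the inclusions "Study service (BH navigation, bridging therapy, CAP consult) ordered in Epic for the patient".
- Sections 5.3.3 and 6 have Epic block control prescribers from these services and refuse any attempt to order one.
- Section 7.1 sets the consult, navigation and bridging orders in the intervention alert to stay unless the prescriber removes them. For navigation it reads: "keep/remove an order for BH navigation for the patient (default = keep").
- Section 5.5 has the CAP told of an ordered consult "prior to eligibility confirmation to avoid any delay". Section 7.3.1 allows three business days for the CAP's review, and 7.3 adds: "The CAP’s recommendations may be noted in the medical record".

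Neither document limits the reviewer to chart content from before the alert, or says that study orders, CAP entries or the prescriber's identity are hidden. Neither plans a comparison of exclusions by arm or an analysis that does not depend on the review.

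**The concern.** Prescribers are randomised first, patients take their prescriber's arm when the alert fires, and the chart review then decides who is in the trial. It is therefore an exclusion made after assignment. Blinding of the reviewer is the only stated protection against exclusions that depend on arm. If the reviewer can see the arm, borderline patients could be kept or dropped differently in the two arms, and an intention-to-treat analysis of those who remain would not repair that. Both primary outcomes are computed on these patients. Protocol 13.4 itself warns, when defending the consent waiver, that systematic exclusion after randomisation would invalidate the findings.

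**Working it through.** The documents state no figure on this point (no expected exclusion rate, no share of patients with a service order), so there is nothing to reproduce. The check is the order of events, followed by an illustration of possible size.

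**Order of events**

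1. The alert fires, or an intervention prescriber orders a study service directly (7.4, Appendix A). The patient is logged on day 0. Any service orders enter Epic at that point, in the intervention arm only.
2. If a consult was ordered, the CAP is told at once (5.5, 7.1) and has three business days (7.3.1).
3. The eligibility reviewer has three business days from logging (7.2), so the two windows overlap.
4. If no consult was ordered, the CAP is told only after eligibility is confirmed (5.5). No CAP note from that route can come first.

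It follows that:

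- **Service order kept:** the checklist, as described, directs the reviewer to an item that reveals the arm.
- **Consult ordered:** a CAP note may also be in the chart, depending on timing and site practice.
- **All orders removed:** nothing in the documents shows the arm, although the absence of orders is partly informative.
- **PI as reviewer:** the PI's own blinding in 5.3.2 has the same weakness.

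The service-order item cannot be required of everyone, because no control patient could meet it. It reads as an alternative entry route (Appendix A), open to one arm only.

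**Illustration of size.** Assume no true effect. Let p be the control rate of use at 6 months and e the extra fraction of intervention patients excluded. The observed intervention rate is then:

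- exclusions unrelated to outcome: p(1−e)/(1−e) = p, no expected shift;
- all excluded are users: (p−e)/(1−e);
- all excluded are non-users: p/(1−e), which drops the share e/(1−p) of that arm's non-users.

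Inputs: 360 per arm is the number remaining at 6 months in Protocol 8.1; 95% is the planned control rate in 8.2.1, and 85% is one of the alternatives there. The 50% rate and all values of e are assumptions. Rejection is from a two-sided 5% unpooled normal test of 360 control against 360(1−e) intervention patients, ignoring clustering.

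| p | e | Who is excluded | Observed rate | OR | Rejection |
|---|---|---|---|---|---|
| 95% | 2% | users | 94.9% | 0.98 | 5.0% |
| 95% | 10% | users | 94.4% | 0.89 | 6.2% |
| 95% | 2% | non-users (2/5 = 40% of them) | 96.9% | 1.67 | 26% |
| 85% | 5% | users | 84.2% | 0.94 | 6.0% |
| 85% | 5% | non-users (5/15 = 33%) | 89.5% | 1.50 | 43% |
| 50% | 10% | users | 44.4% | 0.80 | 31% |
| 50% | 10% | non-users (10/50 = 20%) | 55.6% | 1.25 | 31% |

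Third row in full: 0.95/0.98 = 0.969; OR = (0.969/0.031)/(0.95/0.05) = 1.67 before rounding.

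The distortion can run either way. At the planned 95% rate it is small if users are dropped and larger only if non-users are picked out.

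**The case against.** The strongest reply is that the documents do not describe the reviewer's screen. Section 7.2 calls the review focused, and procedures sit in site manuals (12.1) and a quality plan (12.2) that are not available here. A masked view is possible. Most criteria in 5.2 are factual: age, drug, setting, language, orders in the prior 180 days. Letting staff rather than unblinded prescribers decide eligibility (5.5) is itself a protection. A psychiatrist's note need not reveal the arm, because 5.3.3 allows ordinary CAP discussion with control prescribers and 13.2 says all systems already offer consultation.

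Much of this stands, and it rules out three stronger readings that a reader might infer.

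- **That no review could have been blind.** This holds strictly only where a service order or study CAP note was visible.
- **That the SAP shows arm-dependent judgement**, because it plans a subgroup by "whether participant had an exclusion diagnosis in year prior to baseline" although 5.2 excludes such diagnoses. That variable is still to be built from baseline diagnosis data and may simply capture recorded diagnoses that chart review did not confirm.
- **That the bias could approach half the 10% minimal important difference.** With 400 per arm (the eligible number in 8.1, here assumed logged) and 90% use, dropping 20 non-users gives 360/380 = 94.7%. But that is 20 of 40 non-users, chosen within days of the alert, before their 6-month status exists. Dropping 20 users gives 340/380 = 89.5%.

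What does not stand is that this is only missing detail. The checklist as described contains an item that separates the arms, and no masking step is stated.

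**Conclusion.** The blinding claimed in Protocol 5.2, 5.3.2, 6 and 7.2 is not delivered by the procedure as written. Arm is revealed where a study service order or study CAP note is visible to the reviewer, and not necessarily for other patients. The resulting exclusions could differ by arm. The documents do not show that they did, and give no basis for a direction or size. The illustrated range runs from no expected shift to an odds ratio of 1.67 from a 2% selective loss of non-users at the planned 95% rate. That upper case rests on selection by an outcome that the reviewer could not yet know. The illustration covers the 6-month proportion only; the effect on person-time of use was not calculated. The point warrants a correction and a sensitivity analysis, but does not by itself invalidate the trial.

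**What to change.** **For any further review**, change 7.2. The reviewer judges diagnosis and the other chart criteria from an extract limited to content before the alert, with study orders, CAP entries and prescriber identity masked. The index antipsychotic, encounter setting, temporary-provider status and any service-order entry route are checked by program, outside the reviewer's view. Simply hiding all same-encounter orders would not work, because several criteria in 5.2 depend on them. None of this changes when the CAP is contacted.

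**For patients already reviewed** (the SAP, Secondary analysis VIII, dates the switch-off of the intervention alert to July 1, 2020):

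1. Report logged and excluded counts, with reasons, by arm. Reasons are already recorded under 7.2.
2. Add to the SAP a sensitivity analysis of both primary outcomes on all alert-logged patients who meet coded pre-alert criteria, whatever the review decided, where outcome data can be pulled from the health record. Restricting it to alert-logged patients also sets aside the entry route open to one arm only.
3. Qualify the blinding statement, for eligibility staff and for the PI, unless the sites can show that masking was applied.

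**Cost.** Item 1 is one table. Item 2 needs extra extraction, because Appendix A collects follow-up data for eligible patients, and the SAP records that Secondary analysis VIII was not done because data harvesting was not completed in time. Coded criteria will misclassify some patients, so this stays a sensitivity analysis.
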